
STUDY DESIGN
	
This is a multicenter, randomized, double-blind, placebo-controlled 52-week study with a 6-week post-treatment follow-up phase, evaluating the efficacy and safety of sarilumab in patients with PMR. There are 2 parallel treatment groups with sarilumab 200 mg or placebo plus protocol defined CS tapering regimens of varying durations (as described below).
 
Patients with active PMR will be randomized to the following 2 arms in a ratio of 1:1.
 
 
Group 1: Sarilumab 200 mg once every 2 weeks (q2w) with a 14 week taper of CS.
 
Group 2: Sarilumab matching placebo q2w with a 52 week taper of CS.
 
 
All patients will receive sarilumab 200 mg or placebo for 52 weeks. Upon randomization at baseline, patients will start the protocol defined taper of prednisone of either 14 weeks duration or 52 weeks duration. All patients will receive prednisone 15 mg/day during the initial 2 weeks of the taper.
 
During the initial 12 weeks of prednisone taper, treatment for one flare before Week 12 is permitted if it can be successfully treated with a low dose (<math>\leq 5</math> mg/day) prednisone add-on taper regimen (completed prior to Week 12) and provided that all other sustained remission parameters are met.
 
For the management of predefined neutropenia, thrombocytopenia and alanine aminotransferase increases, study drug (sarilumab/matching placebo) must be temporarily withheld and a request to reduced dosage to sarilumab 150 mg q2w (for patients randomized to the 200 mg q2w arm only)/matching placebo may be made in a blinded manner through IRT system which will implement the request appropriately based upon the patient's treatment assignment, based on investigator judgment.
 
Patients, who experience a flare or persistent disease activity and cannot follow the per protocol CS taper during the 52-week treatment period or the permitted prednisone add-on treatment prior to Week 12, will continue in the study with a CS rescue regimen as determined by the Investigator (as long as it does not pose a safety risk or contraindication with concomitant sarilumab administration) while double-blind injections of sarilumab or matching placebo will continue for the full 52 week treatment period.
 
All patients who prematurely and permanently discontinue study medication will be asked to return to the site for study assessments as per protocol until end of study evaluation.

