Sarilumab, a fully human immunoglobulin G1 (IgG1) monoclonal antibody, targets IL-6R and inhibits IL-6 signaling. In this study, PMR patients will be treated with sarilumab with CS in order to evaluate the efficacy and safety of sarilumab in patients with PMR.

The efficacy and safety of sarilumab have been evaluated in the phase 2 and phase 3 studies of the rheumatoid arthritis (RA) clinical development program across different segments of the RA populations, patients with sarilumab treatment showed clinically relevant and significant improvements compared with placebo or active comparator either in combination with methotrexate or as monotherapy, respectively. Based on the safety profile of sarilumab available to date and other biological DMARDs, important identified risks include serious infections, neutropenia, and hypersensitivity reactions; important potential risks to be considered with sarilumab administration, consistent with this class of therapy, include laboratory abnormalities and the potential clinical consequences, such as thrombocytopenia and the risk of bleeding, clinically evident hepatic injury with elevated hepatic transaminases, and lipid abnormalities and increased risk of MACE. Other potential important risks include increased risk of malignancy and gastrointestinal perforation.

In addition to clinical development for RA, sarilumab has also been studied in patients with ankylosing spondylitis and non-infectious uveitis. Overall, the safety observations from these studies were consistent with what has been observed in patients with RA.

The primary dose of sarilumab for this study/indication (ie, 200 mg subcutaneously [SC]) once every 2 weeks [q2w]) is selected based largely on the aggregate data from the sarilumab rheumatoid arthritis (RA) clinical development program.

Both 200 mg q2w and 150 mg q2w doses have demonstrated robust clinical efficacy responses in the Phase 3 RA clinical development program, and suppression of biological markers of disease and inflammation similar to those found in PMR patients. While the higher dose has a generally more favorable efficacy response, both doses have acceptable safety profiles (see Investigator Brochure for additional details). Therefore, the dose of sarilumab 200 mg q2w is more likely to provide beneficial effects for patients with PMR and is selected for further evaluation in this study.

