##### **10.4.1 Temporary treatment discontinuation with investigational medicinal product (sarilumab or matching placebo)**

Temporary treatment discontinuation may be considered because of suspected AEs. Re initiation of treatment with the IMP (SC and/or oral) will be done under close and appropriate clinical/and or laboratory monitoring once it is considered that the responsibility of the IMP(s) in the occurrence of the concerned event was unlikely and if the selection criteria for the study are still met (refer to [Section 7.1](#) and [Section 7.2](#)).

Temporary SC IMP treatment discontinuation corresponds to  $\geq 1$  dose not administered to the patient.

A temporary discontinuation of SC IMP  $\geq 31$  consecutive days will be considered permanent.

The following is a list of criteria for temporary discontinuation (refer to [Section 10.8](#) for details):

- Increase in ALT level to  $\geq 3$  x ULN to  $\leq 5$  x ULN and total bilirubin  $\leq 2$  x ULN will result in temporary IMP discontinuation. The IMP (sarilumab or matching placebo) can be resumed only after the ALT has returned to a value  $< 3$  x ULN and all requirements for resumption of study drug administration are met based on investigator's judgement. The IMP may be resumed at the same dose or at a lower dose of 150 mg q2w in such cases if the patient was randomized to the 200 mg group (see [Section 10.8.2](#) and [Appendix E](#)).
- Decrease in neutrophil count to a level  $\geq 500/\text{mm}^3$  to  $< 1000/\text{mm}^3$  without signs of infection. The IMP (sarilumab or matching placebo) can be resumed only after the neutrophils have returned to a value  $\geq 1000/\text{mm}^3$  and all requirements for resumption of study drug administration are met based on investigator's judgement. The IMP may be

resumed at the same dose or at a lower dose of 150 mg q2w in such cases if the patient was randomized to the 200 mg group (see [Section 10.8.3](#) and [Appendix E](#)).

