### 10.8.2 Liver function tests

Please refer to [Section 10.5.5](#) for liver function test (LFT) abnormalities to be reported as AESI.

The Sponsor relies on investigators', particularly Safety Assessors', judgment for adapting concomitant medication in case of LFT abnormalities.

In order to closely follow LFTs, assessment of ALT, AST, alkaline phosphatase, and bilirubin (total, conjugated) are performed per specifications on the study flow charts (see flow chart [Section 1.2](#)).

- The IMP (sarilumab or matching placebo) should be permanently discontinued in case of confirmed ALT  $>5$  x ULN or in case of confirmed ALT  $>3$  x ULN and total bilirubin  $>2$  x ULN (unless the patient has documented Gilbert's disease). A complete serological and ultrasonography work-up should be conducted in case of ALT  $>5$  x ULN or ALT  $>3$  x ULN and concomitant total bilirubin  $>2$  x ULN (see [Appendix E](#)).
- If ALT is  $\geq 3$  x ULN and  $\leq 5$  x ULN and bilirubin is  $\leq 2$  x ULN, administration of SC IMP must be temporarily interrupted, and LFTs must be repeated within 48 hours from the study Investigator's awareness for confirmation of transaminase levels. If the elevated ALT level is confirmed but stays below the 5 x ULN thresholds, then LFTs must be repeated according to the provided guideline and at a minimum of every 7 days until conditions for resumption of SC IMP administration are met (see [Appendix E](#)).
- The SC IMP will then be restarted at the Safety Assessor's discretion after conditions for resumption of IMP administration are met (ALT  $<3$  x ULN). Safety assessor will have the options of either to restart the SC IMP at its current dose or to perform a dose reduction

request in a blinded manner through IRT for patients without a previous reduction in dose. Dose of sarilumab will then be reduced to 150 mg if the patient was randomized to the 200 mg group.

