### 10.8.3 Neutrophils

Refer to [Section 10.5.5](#) criteria for reporting neutropenia as an AESI.

In case of a decrease in neutrophil count to a level  $\geq 500/\text{mm}^3$  and  $< 1000/\text{mm}^3$ :

- The IMP (sarilumab or matching placebo) may temporarily discontinued; the patient must be assessed for evidence of infection and CBC blood test repeated within 48 hours from the Safety Assessor's awareness of neutrophil count  $\geq 500/\text{mm}^3$  and  $< 1000/\text{mm}^3$ .
- Discontinuation of SC IMP is maintained until the neutrophil count returns to  $\geq 1000/\text{mm}^3$  (see [Appendix E](#)).
- After the patient meets all requirements for resumption of SC IMP administration, including neutrophil count  $\geq 1000/\text{mm}^3$ , then SC IMP administration may resume. The safety assessor will have the options of either to restart the SC IMP at its original dose or to perform a dose reduction request in a blinded manner through IRT. The dose of sarilumab will be reduced to 150 mg if the patient was randomized to the 200 mg group.

In case of a decrease in neutrophil count  $< 1000/\text{mm}^3$  with signs of infection or neutrophil count  $< 500/\text{mm}^3$ :

- The IMP must be permanently discontinued.
- The patient must be re-assessed for evidence of infection and CBC blood test repeated within 48 hours from the Safety Assessor's awareness of neutrophil count  $< 1000/\text{mm}^3$  with signs of infection or neutrophil count  $< 500/\text{mm}^3$ .
- It is recommended to admit the patient to the hospital in case of neutrophil count  $< 1000/\text{mm}^3$  with suspicion of infection or neutrophil count  $< 500/\text{mm}^3$ .
- The neutrophil count  $< 500/\text{mm}^3$  persisting for more than 5 days are reported as an SAE.

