### 10.8.4 Platelets

Refer to [Section 10.5.5](#) for criteria for reporting thrombocytopenia as an AESI.

In case of a decrease in platelet count to a level  $\geq 50\ 000/\text{mm}^3$  and  $< 100\ 000/\text{mm}^3$ :

- The IMP (sarilumab or matching placebo) must be temporarily discontinued; the patient must be assessed for evidence of spontaneous bleeding and CBC blood test repeated within 48 hours from the Safety Assessor's awareness of platelet count  $\geq 50\ 000/\text{mm}^3$  and  $< 100\ 000/\text{mm}^3$ .
- Discontinuation of SC IMP is maintained until the platelet count returns to  $\geq 100\ 000/\text{mm}^3$  (see [Appendix E](#)).

- After the patient meets all requirements for resumption of SC IMP administration, including platelet count  $\geq 100\ 000/\text{mm}^3$ , then SC IMP administration may resume. The Safety Assessor will have the option of either to restart the SC IMP at its original dose or to perform a dose reduction request in a blinded manner through IRT. The dose of sarilumab will be reduced to 150 mg if patient was randomized to the 200 mg group.

The SC IMP must be permanently discontinued if platelet count is  $< 50\ 000/\text{mm}^3$  (confirmed by repeat testing) or if  $< 100\ 000/\text{mm}^3$  with spontaneous bleeding (see [Section 10.4.2](#)).

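### Protocol 10.8.3 makes the SC study-drug hold optional at neutrophils 500 to <1000/mm3 without infection, while the summary and the parallel ALT and platelet rules make it mandatory

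*Protocol*

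**What the plan says.** Section 10.8.3 sets the rule for neutrophils of at least 500 and below 1000/mm3: "The IMP (sarilumab or matching placebo) may temporarily discontinued". The same bullet requires an assessment for infection and a repeat blood count within 48 hours. The second bullet keeps the drug stopped until the count is back to at least 1000/mm3. Counts below 500/mm3, or below 1000/mm3 with signs of infection, fall under a separate permanent-stop rule. The *may* therefore governs only patients without infection.

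Elsewhere the protocol is firmer:

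- The Clinical Trial Summary, covering predefined neutropenia, thrombocytopenia and ALT increases together, says "study drug (sarilumab/matching placebo) must be temporarily withheld". It gives no numerical range.
- Section 10.8.2, for ALT between 3 and 5 times ULN with bilirubin no more than twice ULN, says "administration of SC IMP must be temporarily interrupted".
- Section 10.8.4, for platelets of at least 50 000 and below 100 000/mm3, says "The IMP (sarilumab or matching placebo) must be temporarily discontinued".
- Section 10.4.1 opens its list with "The following is a list of criteria for temporary discontinuation" and includes this neutrophil range without infection. It adds: "The IMP (sarilumab or matching placebo) can be resumed only after the neutrophils have returned to a value" of at least 1000/mm3.

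Three overview passages are permissive for the laboratory abnormalities as a group: Protocol 6.1, the dose-modification text in Protocol 8.1.1, and SAP 1.1.

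**The concern.** The three predefined laboratory abnormalities are handled in parallel throughout the protocol, yet in the detailed safety instructions only the neutrophil hold is optional. Section 4 states that "important identified risks include serious infections, neutropenia, and hypersensitivity reactions", so the optional hold sits on a recognised risk of the drug. Read literally, 10.8.3 lets a site continue injections in a patient with Grade 3 neutropenia, while a site working from the summary must stop. Two sites could treat the same count differently and each cite the protocol.

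**Working it through.** No computed figure is involved, so the check is a comparison of wording.

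**Range.** 1000/mm3 equals 1000 × 10^6 per litre = 1.0 Giga/L, and 500/mm3 equals 0.5 Giga/L. The 10.8.3 range is thus 0.5 to <1.0 Giga/L, which is Grade 3 in Protocol 11.4.3.2.1.1 and SAP 2.4.5.3.

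**Operative wording side by side.**

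| Place | Abnormality | Hold |
|---|---|---|
| Protocol 10.8.3, first bullet | Neutrophils 500 to <1000/mm3 | *may* |
| Clinical Trial Summary | Neutropenia, thrombocytopenia, ALT | *must* |
| Protocol 10.8.2 | ALT | *must* |
| Protocol 10.8.4 | Platelets | *must* |
| Protocol 10.4.1 | Neutrophils in this range, no infection | listed criterion; resume only after recovery |
| Protocol 10.8.3, second bullet | Neutrophils in this range | presupposes a hold |
| Protocol 6.1, 8.1.1; SAP 1.1 | Laboratory abnormalities generally | left to the investigator |

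**Which reading is intended.** Four features point to *must*.

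1. The 10.8.3 sentence is ungrammatical because *be* is missing. The platelet sentence in 10.8.4 has the same construction with *must be*.
2. The second bullet of 10.8.3 only makes sense if the drug has been stopped.
3. In 10.4.1 the neutrophil and platelet items are built the same way, and 10.8.4 makes the platelet hold mandatory.
4. In the summary, the closing reference to investigator judgment attaches most naturally to the dose-reduction request, which is the part introduced by *may*.

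**Safeguards under either reading.** The infection assessment and the 48-hour repeat count are mandatory. The permanent-stop thresholds in 10.4.3 and 10.8.3 are the same.

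**The case against.** The strongest reply is that the protocol largely answers the question itself. The next bullet and 10.4.1 assume a hold, the safeguards apply regardless, and 10.5.6 sends sites to the Appendix E flow chart, which may state the hold plainly. That chart is not shown in the available text, so it cannot settle the matter either way. The argument limits the practical risk but leaves the conflict in the safety instruction.

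One could also argue that *may* was meant, since 6.1, 8.1.1 and SAP 1.1 are permissive and 10.4.1 begins by saying that temporary discontinuation can be considered. But the three overview passages cover all three abnormalities, so they clash equally with the *must* for ALT and platelets. Moreover, 6.1 and 8.1.1 refer onward to the detailed rules, and SAP 1.1 gives sites no instructions.

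Four stronger readings are tempting but not supported:

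- *Sites continued dosing in Grade 3 neutropenia.* The documents say nothing about what sites did.
- *The wording alters responder status.* Section 10.4.1 says an SC interruption of 31 or more "consecutive days will be considered permanent", and permanent withdrawal from treatment counts as failure of the primary endpoint. But that rule applies to any SC interruption, whether for ALT, platelets, infection or neutrophils. It does not arise from *may* versus *must*.
- *Protocol 11.4.3.2.1.1 contradicts 10.8.3 by saying the dose will be reduced to 150 mg.* Section 10.8.3 ends with nearly the same sentence, describing what follows a reduction request. The copy in the analysis section looks stray and is not a competing dosing rule.
- *Low counts with dosing continued would go unreported.* An asymptomatic case might not qualify as an adverse event under 10.5.3. However, SAP 2.4.5.3 already plans incidence by maximal grade, time to first Grade 3 or 4 neutropenia, and listings flagging PCSA values. SAP Appendix C includes neutrophils below 1.0 Giga/L among the PCSA criteria.

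**Conclusion.** The inconsistency is real and can be confirmed by reading the sections together. In the detailed safety rules, the neutrophil hold alone is optional, against a mandatory hold in the summary and in the ALT and platelet rules. It is probably a drafting slip, although the documents do not say so. It is worth correcting because the literal text permits continued dosing in Grade 3 neutropenia and the correction is one phrase.

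Its reach is narrow: patients with counts of 500 to <1000/mm3 and no infection. The documents give no expected incidence. The required checks and the agreed permanent-stop thresholds limit the hazard. No power, alpha or sample-size figure is affected. SAP 1.1 gives 19 May 2021 as the last patient's last visit, so the correction serves the record and any reuse of this text, and cannot change past conduct. The wording mismatch is certain; whether sites faced a practical conflict depends on the Appendix E chart.

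**What to change.** 1. In the first bullet of Protocol 10.8.3, write that the SC IMP *must be temporarily discontinued*, matching 10.8.4.
2. Confirm that the neutropenia flow chart in Appendix E says the same.
3. Align Protocol 6.1, Protocol 8.1.1 and SAP 1.1 so that, for all three predefined abnormalities, the hold is mandatory and only the later reduction to 150 mg is discretionary.
4. As tidying, delete the stray dose-reduction sentence from Protocol 11.4.3.2.1.1.
5. Optionally, add SC IMP hold status and hold dates to the neutrophil PCSA listing already planned under SAP 2.4.5.3. Protocol 10.4 requires any IMP discontinuation to be documented in the eCRF, and SAP 2.5.3 refers to an SC IMP administration page, so no new data collection is needed.

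The cost is one phrase in 10.8.3, a few matching edits, and, if wanted, extra columns in an existing listing. No analysis changes.

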### 10.8.4 Platelets

Refer to [Section 10.5.5](#) for criteria for reporting thrombocytopenia as an AESI.

In case of a decrease in platelet count to a level  $\geq 50\ 000/\text{mm}^3$  and  $< 100\ 000/\text{mm}^3$ :

- The IMP (sarilumab or matching placebo) must be temporarily discontinued; the patient must be assessed for evidence of spontaneous bleeding and CBC blood test repeated within 48 hours from the Safety Assessor's awareness of platelet count  $\geq 50\ 000/\text{mm}^3$  and  $< 100\ 000/\text{mm}^3$ .
- Discontinuation of SC IMP is maintained until the platelet count returns to  $\geq 100\ 000/\text{mm}^3$  (see [Appendix E](#)).

- After the patient meets all requirements for resumption of SC IMP administration, including platelet count  $\geq 100\ 000/\text{mm}^3$ , then SC IMP administration may resume. The Safety Assessor will have the option of either to restart the SC IMP at its original dose or to perform a dose reduction request in a blinded manner through IRT. The dose of sarilumab will be reduced to 150 mg if patient was randomized to the 200 mg group.

The SC IMP must be permanently discontinued if platelet count is  $< 50\ 000/\text{mm}^3$  (confirmed by repeat testing) or if  $< 100\ 000/\text{mm}^3$  with spontaneous bleeding (see [Section 10.4.2](#)).

### **10.8.5 Systemic hypersensitivity reactions/anaphylaxis**

Severe systemic hypersensitivity reactions (in rare cases, fatal anaphylaxis) have been reported with biologics, including tocilizumab. Rare, severe non-fatal systemic hypersensitivity reactions have been observed with sarilumab. The patient should be monitored for 30 minutes or up to 2 hours as per country specific requirements after the IMP (sarilumab or matching placebo) injection when given at the study site. Also patient should be advised, when IMP is administered at home, to self-monitor for potential signs and symptoms that may suggest a hypersensitive reaction for 30 minutes or up to 2 hours as per country specific requirements after administration. Any problems should be documented in the patient's Home Dosing Diary or in the medical notes and reported as AE. In case of systemic hypersensitivity reaction, the IMP should be discontinued and those events meeting seriousness criteria (eg, hospitalization, life threatening, etc.; see [Section 10.5.1.2](#)) should be reported as SAEs. [Appendix G](#) defines clinical criteria for diagnosing anaphylaxis. If clinical criteria for anaphylaxis are met, appropriate treatment should be administered immediately and the event should be reported as a SAE.

### **10.8.6 Diverticulitis and gastrointestinal perforation**

The Investigator should pay particular attention to gastrointestinal symptoms such as, but not limited to, abdominal pain, hemorrhage, or unexplained change in bowel habits with fever to assure that the diagnosis is not missed and that the conditions are managed appropriately to avoid the complication of perforation. If necessary, the patient should be referred to a specialist.

Corticosteroid use or prior history of diverticulitis is known to increase the risk of gastrointestinal perforations. The Investigator should be aware of this potential risk and monitor any sign of diverticulitis.

Gastro-intestinal perforation will be reported as an SAE (see [Section 10.5.4](#)). Confirmed diverticulitis or gastrointestinal ulceration should be reported as AEs.

### **10.8.7 Management of dyslipidemia**

Patients treated with tocilizumab have been observed to have increased elevations of all lipid parameters, including LDL cholesterol. A similar finding has been observed for sarilumab. The potential cardiovascular effect of the lipid elevations, including LDL levels in this population of PMR patients treated with anti-IL-6R antagonists is unknown.

As such, patients who are found to have dyslipidemia during the course of the study should be treated according to the NCEP/ATP3 or applicable local guideline. Also see [Section 8.8.3](#) under concomitant medication rules for lipid lowering therapy.

#### **10.8.8 Acute renal failure**

Sarilumab is not known to be associated with a clinically significant effect on renal function.

